#### **Body Weight**

Body weight will be measured using the same calibrated scale at each visit (whenever possible). Subjects will be weighed at approximately the same time of day on the same scale, wearing underwear and a gown and without shoes; they will be instructed to empty their bladders before being weighed.

**Note**: If disrobing for weighing is logistically impossible, the subject must be dressed as lightly as possible, with consistency from visit to visit. The study site will be responsible for maintaining the scale during the study. Maintenance of the scale must be documented.

#### **Physical Examination**

A physical examination, including a review of body systems (head and neck, eyes, chest and lungs, cardiovascular, extremities and back, and abdomen examination), will be performed to assure that a subject meets entry criteria. Clinically relevant findings in physical examination must be documented in the source document and in the Medical History section of the eCRF.

#### **Growth Velocity and Tanner Staging**

Growth velocity will be assessed in all subjects during the study.

Tanner staging will be performed in order to assess the physical measurements of sexual development. If at any of the evaluations the subject's sexual maturation is assessed as being Tanner Stage 5, no further evaluations are needed during the study (Attachment 6, Tanner Staging).

#### 9.9. Exploratory Biomarker Evaluations

Fasting plasma, serum, and urine archive samples will be collected (where local regulations permit) at the time points specified in the Time and Event Schedule to allow for biomarker analyses and exploratory research related to canagliflozin or T2DM and obesity. Refer to the laboratory manual for further information regarding the collection and handling of exploratory blood and urine samples.

# 10. SUBJECT COMPLETION, PREMATURE DISCONTINUATION OF TREATMENT, OR WITHDRAWAL FROM THE STUDY

# 10.1. Subject Completion

A subject will be considered to have completed the treatment phase if he or she has completed assessments at Week 52 of the double-blind treatment phase.

Subjects who prematurely discontinue study drug for any reason before completion of the double-blind phase at Week 52 will not be considered to have completed the study.

End-of-treatment evaluations will be performed when the subject completes the double-blind treatment phase at Week 52. The EOT evaluation should be followed by a 30-day off-drug follow-up visit or telephone contact to collect any serious adverse events and adverse events of interest.

If a subject discontinues from study drug prior to Week 52, he or she will be followed as per the assessments included in the Time and Events Schedule up to the Week 52 visit, without the requirement for the post-Week 52 follow-up (see Section 10.2.4, Comprehensive Follow-up at Scheduled Study Visits Following Premature Discontinuation of Study Drug, for more detail).

For details regarding the procedures performed at the EOT evaluation, refer to the Time and Events Schedule.

# 10.2. Study Drug Treatment Premature Discontinuation, Reinstitution, and Follow-up

# 10.2.1. Study Drug Treatment Premature Discontinuation

A subject should discontinue study drug for any of the following reasons:

- Subject is persistently in poor compliance with study drug or procedures.
- The investigator believes that for safety or tolerability reasons it is essential for the subject to discontinue study drug.

- The subject experiences a serious adverse event of biochemically-confirmed DKA (eg, low pH in presence of elevated serum ketones or urine ketones, etc).
- The investigator formally unblinds the subject's study treatment allocation.
- The subject becomes pregnant (study therapy should be immediately interrupted based upon a positive urinary human chorionic gonadotropin [hCG], and permanently discontinued if confirmed by a serum β-hCG test).
- Subject requires disallowed therapy (see Section 8, Prestudy and Concomitant Therapy).
- Subject has an eGFR of <45 mL/min/1.73m^2, confirmed by repeat (no sooner than 7 days and no later than 14 days from the initial report) by the central laboratory.
  - **Note:** For subjects meeting this eGFR discontinuation criterion, a repeat determination should be performed between 7 and 14 days and study drug discontinued if the repeat determination confirms that the value still meets the criteria (unless a reversible acute cause is identified [eg, short-term illness or transient volume depletion] in which case an additional repeat determination can be performed after resolution of the illness). If the value is improving on repeat determination, but still meets the discontinuation criteria, an additional repeat measurement may be performed within 2 weeks, and the subject continued if they no longer meet the criterion or if improvement continues (in which case an additional repeat within 2 weeks may be obtained, and be used to determine subject discontinuation from the study).
- The subject meets the rescue therapy criteria, but the AHA to be initiated as rescue medication is not approved for use in the country of the investigational site, or the subject has a contraindication to the use of any approved AHA to be used as rescue medication, based upon the local label.

All subjects who prematurely discontinue study drug should continue subsequent study visits and post-treatment follow-up evaluations (see Section 10.2.4, Comprehensive Follow-up at Scheduled Study Visits Following Premature Discontinuation of Study Drug and Section 9.1.5, Post-treatment Phase [Follow-up]). Treatment should be recommenced wherever possible and routinely considered at every visit following discontinuation (see Section 10.2.3, Reinstitution of Treatment with Study Drug That Has Been Interrupted).

Subjects and/or parents[s]/legal guardian[s] who decide to discontinue double-blind study drug must be interviewed by the investigator so as to determine if a specific reason for discontinuing study drug can be identified. Subjects should be explicitly asked about the contribution of possible adverse events to their decision to discontinue study drug, and investigators should confirm that any adverse event information elicited has been documented. If a subject elects to discontinue study drug due to an adverse event, the event should be recorded as the reason for study drug discontinuation, even if the investigator's assessment is that the adverse event would not require study drug discontinuation. The reason for study drug discontinuation is to be documented in the eCRF and in the source documentation. Study drug assigned to the subject who discontinued the study may not be assigned to another subject. Subjects who discontinue study drug will not be replaced.

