#### Management of double-blind study drug based on renal function:

- Subjects who have undergone re-randomization and subsequently have a confirmed eGFR <60 mL/min/1.73m^2 will undergo down-titration (or mock down-titration) of blinded study drug at an unscheduled down-titration visit; only those subjects who were re-randomized to the canagliflozin 300 mg dose will actually titrate down (in a blinded fashion via the IWRS). Subjects randomized to canagliflozin 100 mg or placebo will undergo a mock down-titration and will continue on their randomized treatment.
- If at any time during the study, a subject has an eGFR of <45 mL/min/1.73m^2 that is confirmed within 1 week, the subject must be discontinued from study drug. Subjects discontinued from study drug and who do not withdraw consent will remain in the study and will be followed for post-treatment evaluations for the duration of the study.
- Prior to down-titrating or discontinuing canagliflozin due to eGFR <60 mL/min/1.73m^2 or <45 mL/min/1.73m^2, respectively, a repeat determination should be performed within 1 week and study drug down-titrated or discontinued if the repeat determination confirms that the value still meets the criteria (unless a reversible acute cause is identified [eg, short-term illness or transient volume depletion] in which case an additional repeat determination can be performed after resolution of the illness).
- All subjects will receive a new medication kit assignment through the IWRS at the unscheduled
  down-titration visit. The investigator, or qualified assigned designee, will provide the subject with
  double-blind treatment medication, updated instructions on dosing and a new subject diary. The
  subject will be instructed to continue with the diet and exercise regimen and the completion of the
  study diary.

**Note**: Once a subject has up-titrated to canagliflozin 300 mg, down-titration is not allowed unless for confirmed eGFR <60 mL/min/1.73m^2. Therefore, if after up-titration to canagliflozin 300 mg a subject

experiences recurrent hypoglycemia (ie, at least 2 episodes within a 7-day period), consideration should be given to down-titrate background AHA(s) such as insulin (or metformin).

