Re- randomization to Week 52	NOT eligible for re- randomization if:  HbA 1c <7.0% or eGFR <60 mL/min/1.73m 	1 tablet of canagliflozin 100 mg	1 tablet of placebo matching canagliflozin 100 mg
Re- randomization to Week 52	Eligible for re-randomization if:  • HbA 1c $\geq$ 7.0% and eGFR $\geq$ 60 mL/min/1.73m 	1 tablet of canagliflozin 100 mg  AND 1 tablet of placebo matching canagliflozin 300 mg  or 1 tablet of canagliflozin 300 mg  AND 1 tablet of placebo matching canagliflozin 100 mg	1 tablet of placebo matching canagliflozin 100 mg  AND  1 tablet of placebo matching canagliflozin 300 mg

The study drug must be swallowed whole with liquid and not chewed, divided, dissolved, or crushed. If the subject does not take the study drug within 12 hours after the first meal of the day, the dose of study drug should be skipped for that day and the subject should be instructed to take the study drug on the following day before the first meal of the day.

Study drug treatment may be interrupted (eg, for safety and/or tolerability reasons such as hospitalizations for major surgical procedure or serious medical illness). In addition, study drug treatment should be interrupted in clinical situations known to predispose to ketoacidosis

(eg, prolonged fasting due to acute illness or surgery [see Section 9.2.2, Management of Blinded Study Drug During Ketonemia]).

For subjects who develop conditions that are associated with amputations, such as a lower-extremity infection, skin ulcer, osteomyelitis, gangrene, or critical limb ischemia, study drug should be interrupted until the condition has resolved in the opinion of the investigator. In the event of an amputation, restarting of dosing with canagliflozin should only be done after careful consideration of the individual risk:benefit and following discussion with the sponsor.

Study drug treatment interruption, occurring for any reason, will be documented on the eCRF. Study drug should be reinstituted once the subject has recovered and the safety and/or tolerability concern is no longer present.

Study-site personnel will instruct subjects on how to store study drug for at-home use as indicated for this protocol.

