## Management of double-blind study drug based on renal function

- Subjects who have undergone re-randomization and subsequently have a confirmed eGFR <60 mL/min/1.73m^2 will undergo down-titration (or mock down-titration) of blinded study drug at an unscheduled down-titration visit; only those who were up-titrated previously to the canagliflozin 300 mg dose will actually titrate down (in a blinded fashion via the IWRS). Subjects randomized to canagliflozin 100 mg or placebo will undergo a mock down-titration and continue their randomized treatment.
- If at any time during the study, a subject has a confirmed eGFR of <45 mL/min/1.73m^2, the subject must be discontinued from study drug as described in Section 10.2, Study Drug Treatment Premature Discontinuation, Reinstitution and Follow-up. Subjects discontinued from study drug and who do not withdraw consent will remain in the study and followed as described in Section 10.2. Study Drug Treatment Premature Discontinuation, Reinstitution, and Follow-up.
- Prior to down-titrating or discontinuing canagliflozin due to confirmed eGFR <60 mL/min/1.73m² or <45 mL/min/1.73m², respectively, a repeat determination should be performed within 1 week and study drug down-titrated or discontinued if the repeat determination confirms that the value still meet the criteria (unless a reversible acute cause is identified [eg, short-term illness or transient volume depletion] in which case an additional repeat determination can be performed after resolution of the illness).
- All subjects will receive a new medication kit assignment through the IWRS at the unscheduled down-titration visit. The investigator, or qualified assigned designee, will provide the subject with double-blind treatment medication with updated instructions on dosing and a new subject diary. The subject will be instructed to continue with the diet and exercise regimen and the completion of the study diary.

**Note:** Once a subject has up-titrated to canagliflozin 300 mg, down-titration is not allowed unless for confirmed eGFR <60 mL/min/1.73m^2. Therefore, if after up-titration to canagliflozin 300 mg a subject experiences recurrent hypoglycemia (ie, at least 2 episodes within a 7-day period), consideration should be given to down-titrate background AHA(s) such as insulin (or metformin).

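### The eGFR <45 stopping rule is stated inconsistently in the protocol: the repeat window differs (within 1 week, or 7 to 14 days), and only Section 10.2.1 lets a subject who is still below 45 but improving continue

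*Protocol*

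**What the plan says.** The rule for an eGFR below 45 mL/min/1.73 m² appears in three places in the protocol. The SAP does not state it.

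- **Synopsis, management of study drug based on renal function.** For an eGFR below 45 "that is confirmed within 1 week, the subject must be discontinued from study drug". The next bullet covers both the down-titration threshold of 60 and the stopping threshold of 45. It again asks for a repeat within a week, and it allows a further repeat only where a reversible acute cause is found.
- **Section 9.1.4.3, same sub-heading.** The below-45 bullet gives no time limit and says "the subject must be discontinued from study drug as described in Section 10.2". The next bullet covers both thresholds: "a repeat determination should be performed within 1 week and study drug down-titrated or discontinued if the repeat determination confirms". A reversible acute cause is again the only exception.
- **Section 10.2.1.** A reason to stop study drug is an eGFR below 45, "confirmed by repeat (no sooner than 7 days and no later than 14 days from the initial report) by the central laboratory". The Note beneath restates the 7-to-14-day window and keeps the reversible-cause exception. It then adds a second one: if the repeat is improving but still below 45, a further measurement "may be performed within 2 weeks, and the subject continued if they no longer meet the criterion or if improvement continues". Where improvement continues, "an additional repeat within 2 weeks may be obtained, and be used to determine subject discontinuation from the study".

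**The concern.** This is a safety stopping rule in subjects aged 10 to under 18, and the three statements of it cannot all be followed in general.

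First, a site that repeats the test promptly, as the Synopsis asks, has no valid confirmation under Section 10.2.1 unless the repeat falls on day 7 or later. A site that follows Section 10.2.1 and repeats on day 10 has missed the Synopsis window.

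Second, the outcome can differ and not only its timing. Take a subject with no acute cause whose repeat is still below 45 but higher than the first value. The Synopsis requires study drug to be discontinued; Section 10.2.1 permits it to continue. Two sites acting in good faith could treat the same finding in opposite ways.

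**Working it through.** The plan gives no derived figure to reproduce, so the check is a side-by-side reading plus day arithmetic. Day 0 is the initial report.

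| | Synopsis | Section 9.1.4.3 | Section 10.2.1 |
|---|---|---|---|
| Confirming repeat | within 1 week | within 1 week (repeat bullet); the below-45 bullet points to Section 10.2 | day 7 to day 14 from initial report |
| Start of clock | not stated | not stated | initial report |
| Reversible acute cause | exception | exception | exception |
| Still below 45 but improving | no exception | none in its own text | further repeats; may continue |
| Laboratory for the repeat | not named | not named | central |

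**1. Windows.** Assume the 1-week clock also starts at the initial report.
- Synopsis and 9.1.4.3: days 1 to 7.
- Section 10.2.1: days 7 to 14.
- Shared: day 7 only.
- Days 1 to 6 (6 days) fit only the Synopsis and 9.1.4.3; days 8 to 14 (7 days) fit only Section 10.2.1.

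**2. Latest decision day, no reversible cause.**
- Synopsis and 9.1.4.3: day 7.
- Section 10.2.1, value not improving: day 14, which is 14 − 7 = 7 days later.
- Section 10.2.1, value improving: this depends on where each 2-week allowance starts, which the Note does not say.
  - From the initial report: the limit stays at day 14.
  - From the previous repeat: 14 + 14 = day 28 for the further repeat, and 28 + 14 = day 42 for the optional last one.
  - Range: day 14 to day 42, or 7 to 35 days after day 7.
  - If improvement continues and the optional last repeat is not taken, the Note sets no final decision day.

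**3. Does the cross-reference resolve it?** The below-45 bullet in Section 9.1.4.3 sends the reader to Section 10.2, so the improving route could be read in there. The bullet that follows still says 1 week and gives the single exception, so Section 9.1.4.3 disagrees with the section it cites. The Synopsis renal rule has no cross-reference, and no passage says which text prevails.

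**4. Laboratory.** Section 10.2.1 names the central laboratory. Attachment 7 assigns the listed tests, including serum creatinine, to the central laboratory and has it report eGFR. The COVID-19 Appendix permits an accredited local laboratory when central testing is not possible, and gives eGFR as an example. The Synopsis and Section 9.1.4.3 are silent on the laboratory for the repeat, and silence is compatible with Section 10.2.1.

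**The case against.** The case for leaving this alone has several sound parts.

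- **One course satisfies every passage.** On the common clock, a central-laboratory repeat on day 7, with drug stopped if the value is confirmed, breaches nothing. The improving route is permissive, and Section 10.2.1 separately lets the investigator stop drug for safety or tolerability. This stands, but it depends on hitting one day and declining an option that the protocol offers.
- **Few subjects may reach the rule.** Exclusion criterion 9 bars an eGFR below 60, so falling below 45 takes a drop of more than (60 − 45)/60 = 25% from entry. This limits the scope; it does not reconcile the text.
- **Early repeats are supported elsewhere.** Section 9.8 provides central-laboratory alerts for follow-up, and Attachment 7 mentions repeating an abnormal result. Neither sets a confirmation window, so the conflict remains.

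Four stronger readings are tempting, and the documents do not support them.

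- **That the laboratory requirement is a third contradiction.** The Synopsis and Section 9.1.4.3 name no laboratory for the repeat, so they do not contradict Section 10.2.1.
- **That Section 10.2.1 adds up to 35 days of exposure.** The 35 days rest on one reading of the clock and count days to a decision. The documents do not say whether dosing continues while repeats are pending. Section 6.1.2 allows a pause without requiring one here: "Study drug treatment may be interrupted (eg, for safety and/or tolerability reasons".
- **That no repeat date can ever satisfy both windows.** Day 7 does on a common clock. The Synopsis and Section 9.1.4.3 leave the start of their week unstated, so a wider or narrower overlap cannot be established.
- **That the closing words of the Note remove the subject from the study.** The Synopsis says "Subjects discontinued from study drug and who do not withdraw consent will remain in the study", Section 10.2.1 goes on to require continued visits, and Section 10.3 does not list this as a withdrawal reason.

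**Conclusion.** The inconsistency is real and confined to two points: the window for the confirming repeat, and what happens when the repeat is still below 45 but improving. On the first, the windows share one day if both run from the initial report. On the second, the Synopsis requires stopping where Section 10.2.1 permits continuation, with a latest decision anywhere from day 14 to day 42, or no set day, against day 7.

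The result assumes a common clock, leaves reversible acute causes aside, and spans both readings of the 2-week allowances.

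A reader might also infer a threat to the primary result, because treatment discontinuation is an intercurrent event (SAP 5.2.2) and determines how a missing Week 26 value is imputed (SAP 5.2.3). That is not shown. The estimand uses treatment policy, the number of subjects affected cannot be derived, and no effect on the primary estimate is claimed. The case for acting rests on uniform handling of a renal safety rule and on avoidable protocol deviations.

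**What to change.** Reconcile the Synopsis, Section 9.1.4.3 and Section 10.2.1 so that the same text appears in all three:

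- one window for the confirming repeat, with its starting point stated;
- one rule for a value confirmed below 45, saying whether the improving exception applies and, if it does, where each 2-week allowance starts and when the decision becomes final;
- laboratory wording consistent with Attachment 7 and with the local-laboratory allowance in the COVID-19 Appendix.

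The choice of clinical rule belongs to the sponsor's clinicians, and no view is offered on it here. The cost is a clarification memo or amendment text, with no new procedure.

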# 10.2.2. EOT and 30-Day Follow-up Assessments for Subjects Who Prematurely Discontinue Study Drug

If a subject discontinues study drug for any reason before the end of the 52-week double-blind phase, EOT and 30-day post-treatment follow-up assessments should be obtained and scheduled assessments should be continued.

Subjects who prematurely discontinue study drug will require an immediate EOT assessment (either on the day of study drug discontinuation or as soon as possible following study drug discontinuation) as well as an off-drug follow-up assessment (ie, clinic visit or telephone contact) approximately 30 days after their last dose of study drug. The Time and Events Schedule describes the evaluation required. If for some reason the subject is unable to be seen within 30 days after discontinuing study drug, the EOT visit may be omitted, but a 30-day off-drug follow-up assessment should be performed.

If a subject discontinues from study drug prior to Week 52, he or she will be followed as per the assessments included in the Time and Events Schedule (see Section 10.2.4, Comprehensive Follow-up at Scheduled Study Visits Following Premature Discontinuation of Study Drug, for more detail).

### 10.2.3. Reinstitution of Treatment with Study Drug that has Been Interrupted

Subjects for whom study drug is interrupted as a result of an adverse event, a life event, or other unforeseen circumstance should be encouraged to restart study drug unless there is a clear contraindication at the discretion of the investigator with concurrence from the sponsor's medical monitor.

Study drug interruption, occurring for any reason, will be documented on the appropriate eCRF.

